8.2. Schedule of Visits and Assessments

The schedule of assessments is shown in Table 3.

A visit window of ± 2 days is permitted throughout the Treatment Period and the Follow-up Period (Visits 2-30). For a missed visit, the site should attempt to contact the subject to reschedule.

Premature discontinuation procedures are provided in Section 7.3.

On Day 3, study staff will check in with outpatient subjects by phone to determine if a dose increase to ALKS 3831 15/10 or 20/10 is needed. If, in the opinion of the Investigator, a dose increase is warranted, an Unscheduled Visit will be arranged mid-Week 1. The following procedures will be performed during the Unscheduled Visit: study drug return, adherence review, and study drug dispensation.

Dose adjustments can only occur on-site and require subjects to come to the study center. Throughout the study, subjects requiring dose adjustments between scheduled visits may arrange an Unscheduled Visit (same procedures as mid-Week 1 Unscheduled Visit described above).

Table 3:Schedule of Assessments

												0	pen I	abel	Trea	tmen	t Peri	iod											u	low- 1p riod
Visit ^a	1 ^b	2 [°]	3	4	5	6	7	8	9	10	11	12	13	14	15	16	17	18	19	20	21	22	23	24	25	26	27	28/ ET/ EOT	29 ^d	30
Study week	-	1	2	4	6	8	10	12	14	16	18	20	22	24	26	28	30	32	34	36	38	40	42	44	46	48	50	52	54	56
Informed Consent	х																													
Eligibility Criteria	x																													
Pregnancy Testing ^e	х							Х						Х						Х										
Urine Drug Screen	Х																													
Weight		Х	Х	Х	Х	Х		Х		Х		Х		Х		Х		Х		Х		Х		Х		Х		Х		Х
Waist Circum- ference		Х	х	х	х	Х		Х		Х		Х		Х		Х		Х		Х		Х		Х		Х		Х		X
Vital Signs ^g		Х	Х	Х	Х	X		Х		Х		Х		Х		Х		X		Х		Х		Х		Х		Х		Х
Laboratory Samples ^h				Х				Х						Х						Х								Х		
ECG				Х				Х						Х						Х								Х		
Physical Exam				X				Х						Х						Х								Х		
PANSS ⁱ				Х		Х		Х						Х						Х								Х		
CGI-S				Х		Х		Х		Х		Х		Х		Х		Х		Х		Х		Х		Х		Х		
AE ^j		Х	Х	Х	Х	Х	Х	Х	Х	Х	Х	Х	Х	Х	Х	Х	Х	Х	Х	Х	Х	Х	Х	Х	Х	Х	Х	Х	Х	Х
ConMed ^j		Х	Х	Х	Х	Х	Х	Х	Х	Х	Х	Х	Х	Х	Х	Х	Х	Х	Х	Х	Х	Х	Х	Х	Х	Х	Х	Х	Х	Х
C-SSRS ^k		Х	Х	Х	Х	Х	Х	Х	Х	Х	Х	Х	Х	Х	Х	Х	Х	Х	Х	Х	Х	Х	Х	Х	Х	Х	Х	Х	Х	Х

Table 3:Schedule of Assessments (Continued)

												Ор	en La	abel T	reati	ment	Perio	d											Foll u Per	р
Visit ^a	1 ^b	2°	3	4	5	6	7	8	9	10	11	12	13	14	15	16	17	18	19	20	21	22	23	24	25	26	27	28/ ET/ EOT	29 ^d	30
Study week	-	1	2	4	6	8	10	12	14	16	18	20	22	24	26	28	30	32	34	36	38	40	42	44	46	48	50	52	54	56

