9. TREATMENT OF SUBJECTS

9.1. Study Drug Dose and Administration

Study drugs include:

• ALKS 3831 10/10 (10 mg olanzapine/10 mg samidorphan), 15/10 (15 mg olanzapine/10 mg samidorphan), or 20/10 (20 mg olanzapine/10 mg samidorphan) administered as a coated bilayer tablet

At Visit 1 and all subsequent visits until EOT, subjects will be given blister cards containing study drug to take at home. Subjects will be instructed to take one tablet by mouth each day, preferably at bedtime. Dosing may be switched to another time, at the Investigator's discretion, if there are tolerability problems; however, frequent switching is discouraged.

Subjects will be instructed to keep all unused tablets in their blister card and to return unused tablets to the study site at their next visit. If dosing is to occur at that visit, the dose should be taken from the subject's next blister card, not from the card they are returning.

If a dose is missed or forgotten, subjects will be instructed to resume regular dosing the following night. Subjects will be instructed not to take a double dose to try to "make up" for the missed dose.

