3.8.2. Efficacy Analysis

The following endpoints will be used to evaluate durability of treatment effect and summarized by treatment sequence and overall for FAS population:

- Change from baseline in PANSS total score, and subscale scores (positive, negative, and general psychopathology subscales) by visit
- Change from baseline in PANSS Excited Component (EC) score (comprised of 5 items, P4. excitement, G4. tension, P7. hostility, G8. uncooperativeness, and G14. poor impulse control) by visit
- Change from baseline in PANSS Marder factor scores by visit
- Change from baseline in CGI-S by visit
- Proportion of Subjects with PANSS response ($\geq 30\%$ improvement from baseline in PANSS total score)
- Time to first relapse
- Time to first remission
- Time to discontinuation

In general, continuous and categorical endpoints will be summarized using descriptive statistics by treatment sequence and overall. Change from baseline within the treatment sequence and overall may also be tested using an one-sample t-test.

The PANSS Marder factor model² consisted of the following 5 factors:

- Negative symptoms
 - N1. blunted affect
 - N2. emotional withdrawal
 - N3. poor rapport
 - N4. passive social withdrawal
 - N6. lack of spontaneity
 - G7. motor retardation
 - G16. active social avoidance
- Positive symptoms
 - P1. delusions
 - P3. hallucinatory behavior
 - P5. grandiosity
 - P6. suspiciousness
 - N7. stereotyped thinking
 - G1. somatic concern
 - G9. unusual thought content
 - G12. lack of judgment and insight
- Disorganized thought
 - P2. conceptual disorganization
 - N5. difficulty in abstract thinking
 - G5. mannerisms and posturing
 - G10. disorientation
 - G11. poor attention
 - G13. disturbance of volition
 - G15. preoccupation
- Uncontrolled hostility/excitement
 - P4. excitement
 - P7. hostility

- G8. uncooperativeness
- G14. poor impulse control
- Anxiety/depression
 - G2. anxiety
 - G3. guilt
 - G4. tension
 - G6. depression

Stabilization is defined as meeting all of the following stabilization criteria:

- PANSS total score ≤ 80
- PANSS score ≤ 4 on each of the following items:
 - P2: conceptual disorganization
 - P3: hallucinatory behavior
 - P6: suspiciousness
 - G9: unusual thought content

After a subject achieves stabilization, relapse and remission are defined as following:

- Relapse: $\geq 30\%$ increase in PANSS total score or re-hospitalization for psychotic symptoms.

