- Remission: PANSS score ≤ 3 (mild or less) on each of the following items in two consecutive efficacy assessments
 - P1: delusions
 - G9: unusual thought content
 - P3: hallucinatory behavior
 - P2: conceptual disorganization
 - G5: mannerisms/posturing
 - N1: blunted affect
 - N4: social withdrawal
 - N6: lack of spontaneity

Time to first relapse will be estimated using the Kaplan-Meier method by treatment sequence and overall. It is defined as the time from the date of stabilization to the date of first relapse. Subjects who completed the treatment without relapse will be censored at the date of last dose. Time to first remission will be analyzed similarly.

Time to treatment discontinuation will be analyzed similarly using the Kaplan-Meier method by treatment sequence and overall. Both all cause discontinuation and discontinuation due to AE will be summarized. For prematurely discontinued subjects (all cause or due to AE), time to event is defined as time from the date of first dose of study drug to the date of last dose of study drug. Other subjects will be censored at the last dose of the study drug.

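### SAP 3.8.2 censors event-free completers at last dose, normally the day before the Week 52 PANSS, which can inflate the last Kaplan-Meier steps for relapse

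*SAP*

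**What the plan says.** SAP 3.8.2 defines relapse, in a subject who has stabilized, as a rise of at least 30% in PANSS total score "or re-hospitalization for psychotic symptoms". On the time to first relapse it says: "It is defined as the time from the date of stabilization to the date of first relapse". On censoring it says: "Subjects who completed the treatment without relapse will be censored at the date of last dose". On remission it adds: "Time to first remission will be analyzed similarly". Remission requires low scores on eight PANSS items "in two consecutive efficacy assessments".

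The SAP does not say:
- on what date a PANSS-defined relapse is counted;
- which of the two assessments dates a remission;
- when a stabilized subject who stops early without relapse is censored;
- at what time the curve is read.

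The Protocol supplies the timing. Table 3 schedules the PANSS at Weeks 4, 8, 12, 24, 36 and 52, and shows no dispensing at Visit 28 (Week 52). Section 9.1 says: "Subjects will be instructed to take one tablet by mouth each day, preferably at bedtime". It allows exceptions: "Dosing may be switched to another time". It also says that a dose taken at a visit comes from the subject's next blister card, and at Visit 28 there is no next card. Section 8.2 allows each visit to move by 2 days either way. Visit 1 may follow the last visit of the antecedent study (ALK3831-A305) by up to 7 days, and that visit supplies the baseline PANSS.

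**The concern.** Events and censoring run on different clocks. Take two subjects who stabilized on the same day and attend Visit 28 on the same day. The one found to have relapsed has the event on the visit date. The other is normally censored the day before, and so is missing from the risk set when the first subject's event is counted. Nothing elsewhere in the SAP reconciles the two dates.

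Relapse is one of the endpoints named for durability of effect, and Protocol 14.5 has the relapse rate estimated by Kaplan-Meier with a plot. With no read-out time fixed, the end of the curve may be taken as the one-year rate, and that is where the mismatch acts. The curves by treatment sequence could also differ in their tails through dosing time or entry gap alone.

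**Working it through.** The plan gives no relapse rate or power to reproduce. The check is a hand calculation of the Week 52 steps, then simulation.

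**Hand calculation, all visits on one day.** Assume 200 subjects with the same stabilization date reach Week 52 and 5 relapses are first seen there.
- SAP rule: 195 are censored the day before, so the risk set is 5 and the step is 5/5 = 100%.
- Censoring at the visit: 5/200 = 2.5%.

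**Hand calculation, visits spread evenly over Days 362 to 366.** Each day has 40 visits, with 1 relapse and 39 event-free subjects.
- SAP rule: the risk sets at the five events are 161, 121, 81, 41 and 1. Through Day 364 the drop is 1 − (160/161)(120/121)(80/81) = 2.7%. Through Day 365 it is 5.0%. On Day 366 it is 100%.
- Censoring at the actual visit date: the risk sets are 200, 160, 120, 80 and 40. The total drop is 1 − (199/200)(159/160)(119/120)(79/80)(39/40) = 5.6%.
- Nominal week: 5/200 = 2.5%.

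So most of the damage is on the last window days, the Day 364 reading is about right, and scatter in visit dates inflates the tail even after the censoring date is moved to the visit.

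If the visit day is random, the curve ends at 100% whenever any of k Week 52 relapses falls on the last window day. The probability is 1 − 0.8^k: 36% for k = 2, 67% for k = 5, 89% for k = 10.

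**Simulation.** From the documents: PANSS weeks, ±2-day window, 0 to 7 day entry gap, about 390 subjects. Assumed: 35% dropout per year, 15% relapse risk per year, 80% stable at baseline, 130 per sequence (one third each), PANSS relapses dated at the visit, no re-hospitalization relapses. There were 150 runs per row (Monte Carlo error up to about 4 points). The entry gap, where used, applies to half the subjects. Entries are the median end-of-curve relapse estimate.

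| N | Setting | SAP rule | Censor at actual Visit 28 date | SAP-rule runs ending at 100% |
|---|---|---|---|---|
| 390 | all visits on nominal day | 100% | 16% | 100% |
| 390 | ±2 days | 100% | 21% | 80% |
| 390 | ±2 days, 20% dose on visit day | 38% | 21% | 0% |
| 390 | ±2 days, entry gap | 29% | 24% | 11% |
| 130 | ±2 days | 25% | 19% | 37% |
| 130 | ±2 days, 20% dose on visit day | 31% | 21% | 7% |
| 130 | ±2 days, entry gap | 23% | 20% | 7% |

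With only 30% stable at baseline, the N = 390, ±2-day setting ends at 100% in 53% of runs instead of 80%. A subject who stabilizes later has a shorter time at Week 52, when earlier stabilizers are still at risk. With a 5% risk instead of 15%, the share in that setting is 48% (80% stable) or 21% (30% stable).

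A second simulation (15% risk, 35% dropout, 100 runs per setting) gave 22% to 34% once some visit-day dosing or late entry was allowed, with 0% to 15% of runs at 100%. Read at Day 364 it gave 14% to 17%. Censoring at the actual Visit 28 date gave 19% to 26%; nominal PANSS weeks gave 15% to 18%.

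**The case against.** A reader might infer that these curves will usually end at 100%. The documents do not support that. It needs nearly everyone to dose at bedtime and to enter on the day they leave the antecedent study. The Protocol makes bedtime only a preference and allows a gap of up to 7 days.

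Nor does the one-day rule explain the whole excess. In a further simulation with 10% dosing on the visit day and 30% entering 1 to 7 days late (200 runs per setting), the SAP rule gave 29% against 24% with censoring at Visit 28 (N = 390), and 24% against 21% (N = 130). With 40% of relapses arising by re-hospitalization, which is not tied to Visit 28, the figures were 24% against 21% (N = 390), and 19% to 21% against 18% to 19% (N = 130). There the rule itself adds about 1 to 5 points; the rest is visit-date scatter in the tail.

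Three further limits stand.
- Neither document says that the end of the curve is the reported figure.
- Dating a PANSS relapse at the visit is the natural reading, but it is an inference.
- If remission is dated at the first of its two assessments, one confirmed at Week 52 is dated Week 36 and escapes the problem.

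It is also tempting to say that a subject first stabilized at Visit 28 gets a time of −1 day. The SAP states no counting convention for these times (with inclusive counting it is 0), and such a subject adds nothing to any risk set.

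Finally, the sole objective is safety and tolerability, and these are descriptive efficacy curves. That limits the importance. It does not make the censoring rule right.

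**Conclusion.** The censoring rule is wrong as written and should be fixed, but it is not critical to the trial. In the settings run, it biased the end of the relapse curve upward or left it unchanged. For a true 15%, the worst case is 100%. More typical values are about 22% to 34% when some subjects dose on the visit day or enter late; one such setting gave 38%, and an admixture of re-hospitalization relapses brought the smaller groups down to 19% to 21%. Part of each excess belongs to visit-date scatter.

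The effect is strongest for subjects stable at baseline. It reaches remission only if remission is dated at the confirming assessment. With visits spread over the window, a Day 364 reading is about right, but nothing in the SAP requires one.

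The direction rests on the SAP's censoring rule, the Protocol's dosing and dispensing schedule, and dating of PANSS relapses at the visit. The sizes rest on the assumed relapse risk, dropout, share stable at baseline, dosing times and entry gaps, none of which the documents give.

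**What to change.** In SAP 3.8.2:

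1. State the event date for a PANSS-defined relapse, and which of the two assessments dates a remission.
2. Censor every stabilized subject without the event, including those who stop early, at the last PANSS assessment instead of the last dose.
3. Use nominal PANSS weeks for both PANSS-dated events and censoring, or an interval-censored estimator. Say how a PANSS at an Early Termination visit is placed. Moving the censoring date to the actual Visit 28 date alone leaves the scatter problem.
4. Keep actual dates for re-hospitalization.
5. Report the Week 52 estimate, not the end of the curve.

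The cost is SAP wording and a few lines of programming before database lock, with no new data.

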5.3. Study Rationale

Phase 1 and Phase 2 studies (ALK33-301 and ALK3831-302, respectively) have demonstrated that ALKS 3831 significantly attenuates olanzapine-induced weight gain while providing similar antipsychotic efficacy for stabilization of schizophrenia symptoms. Safety and tolerability data from these studies indicate that ALKS 3831 is safe and generally well-tolerated. However, the longest treatment period assessed to date is 24 weeks. The proposed study will extend these findings and evaluate the safety and tolerability of ALKS 3831 over a 52-week period.

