7.3. Subject Withdrawal

A subject may be discontinued from the study at any time if the subject, Investigator, or the Sponsor determines that it is not in the best interest of the subject to continue participation. If a subject has an absolute neutrophil count (ANC) $< 1.0 \times 10^3$ per µL or HbA1c $\geq 6.5\%$ at any time during this extension study, the subject will be discontinued from the study. Other reasons for discontinuation include the following:

- AEs
- Lack of Efficacy
- Lost to follow-up
- Withdrawal by subject

- Protocol Deviation (noncompliance with study drug or study procedures)
- Pregnancy
- Study terminated by Sponsor
- Other

If a subject withdraws from the study for any reason, any ongoing AEs will be followed until resolution, until deemed stable by the Investigator, or until the subject is deemed by the Investigator to be lost to follow-up. If, in the opinion of the Investigator, it is necessary to monitor a subject beyond the Safety Follow-up Visit, the Follow-up Period may be extended, as necessary. In such instances, the Sponsor and the Investigator will agree to an acceptable follow-up schedule.

In the event that a subject chooses to withdraw from the study, the Investigator should make a reasonable effort to ascertain the reason(s) for withdrawal, while fully respecting the subject's rights. Enrolled subjects are to be asked to return to the clinic for an Early Termination (ET) Visit and to complete a subsequent Safety Follow-up Period. The ET Visit should be scheduled as close as possible to the subject's last dose and will mimic the assessments scheduled to be conducted at the End of Treatment (EOT) Visit (Visit 28, Table 3). If the subject fails or refuses to return to the study center, an attempt must be made to contact the subject by telephone in order to assess as many safety and efficacy parameters as possible. All data collected over the telephone must be documented and kept in the subject's record.

The Investigator must maintain a record of all subjects who fail to complete the study. The reason for study discontinuation will be documented and entered on the appropriate electronic case report form (eCRF). If a subject is lost to follow-up, a reasonable attempt to contact the subject must be made and documented.

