14.1. Sample Size Considerations

No formal sample size calculation was performed for this extension study. A sample size of approximately 390 subjects is based on the estimated maximum number of subjects who might be expected to continue from the ALK3831-A305 study.

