14.5. Efficacy Analysis

Efficacy analyses will be carried out using the FAS Population. The following endpoints will be used to evaluate durability of treatment effect:

- Change from Baseline in PANSS total score and subscales by visit
- Change from Baseline in CGI-S by visit
- PANSS response
- Relapse
- Remission
- Time to discontinuation

The PANSS (total and subscale scores) and CGI-S scores, and appropriate changes from Baseline, will be summarized using descriptive statistics. Positive and Negative Syndrome Scale response and remission at each visit will be summarized as number and percentage.

The discontinuation rate and the relapse rate will be estimated using the Kaplan-Meier (KM) Method and the KM plot will be provided.

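### The Kaplan-Meier curve for discontinuation due to AE censors subjects who stop for other reasons, so its complement can overstate the share who stop for an AE

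*SAP*

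**What the plan says.** SAP 3.8.2 names the estimator: "Time to treatment discontinuation will be analyzed similarly using the Kaplan-Meier method by treatment sequence and overall". It applies it to two endpoints: "Both all cause discontinuation and discontinuation due to AE will be summarized". The event is defined for both at once ("For prematurely discontinued subjects (all cause or due to AE), time to event is defined as time from the date of first dose", running to the last dose), and everyone else falls under one rule: "Other subjects will be censored at the last dose of the study drug".

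Protocol 14.5 describes the output as a rate: "The discontinuation rate and the relapse rate will be estimated using the Kaplan-Meier (KM) Method and the KM plot will be provided". It lists time to discontinuation among the efficacy endpoints, which are analysed in the FAS.

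Protocol 7.3 shows how many other ways out there are. Under "Other reasons for discontinuation include the following" it lists, besides AEs, lack of efficacy, loss to follow-up, withdrawal by the subject, protocol deviation, pregnancy, sponsor termination and other.

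Two crude summaries are also planned. SAP 3.3 gives numbers and percentages discontinuing by reason, and SAP 3.9.1 gives numbers and percentages with AEs leading to discontinuation of treatment. Neither document mentions competing risks or cumulative incidence.

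**The concern.** For the all-cause endpoint the censoring rule is harmless, because the subjects left to censor are the completers. For the AE endpoint the same sentence also censors every subject who stopped for a non-AE reason. Kaplan-Meier treats a censored subject as still able to have the event later, with the same risk as those who remain. Someone who has already stopped study drug for lack of efficacy cannot later stop it for an AE.

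One minus Kaplan-Meier then estimates the risk of stopping for an AE if nobody stopped for any other reason, and does so only if the reasons for stopping are independent. The SAP does not state that assumption, and it is hard to defend here: dosing is adjusted for tolerability (Protocol 8.1), and the protocol's background says that tolerability problems affect compliance and retention on olanzapine (Protocol 5.1).

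At stake is how a tolerability curve is read in a study whose objective is long-term safety and tolerability. The curve can end above the percentage in the AE tables with no explanation. Because results are shown by treatment sequence, sequences with equal AE discontinuation can also appear to differ.

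**Working it through.** **Inputs.** The treatment period is 52 weeks (Protocol 5.3: "evaluate the safety and tolerability of ALKS 3831 over a 52-week period"). About 390 subjects are planned (Protocol 14.1: "No formal sample size calculation was performed for this extension study"). The documents state no expected discontinuation rate, so there is no planned figure to reproduce. The shares below are assumptions: A is the true share stopping for an AE by week 52, and O is the share stopping for any other reason.

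**Step 1: constant cause-specific hazards.** The total cumulative hazard is H = −ln(1 − A − O), of which the AE part is H × A/(A + O). Hence

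1 − KM = 1 − exp(−H × A/(A + O)) = 1 − (1 − A − O)^(A/(A + O)).

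For A = 10% and O = 30%: H = −ln(0.60) = 0.511, the AE part is 0.511 × 0.25 = 0.128, and 1 − exp(−0.128) = 12.0%.

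**Step 2: limits set by timing.** If every AE stop comes before every other stop, 1 − KM = A. If every other stop comes first, the AE stops occur among the remaining share 1 − O, and 1 − KM = A/(1 − O). These are the smallest and largest values.

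| True AE share A | Other O | Total | 1 − KM, constant hazards | Relative excess | Limits from timing |
|---|---|---|---|---|---|
| 10% | 20% | 30% | 11.2% | 12% | 10.0% to 0.10/0.80 = 12.5% |
| 10% | 30% | 40% | 12.0% | 20% | 10.0% to 0.10/0.70 = 14.3% |
| 10% | 40% | 50% | 12.9% | 29% | 10.0% to 0.10/0.60 = 16.7% |
| 10% | 50% | 60% | 14.2% | 42% | 10.0% to 0.10/0.50 = 20.0% |

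Over A = 5% to 15% and O = 10% to 50%, the constant-hazard excess runs from 0.3 to 6.5 percentage points.

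**Step 3: simulation at N = 390** (200 runs per case, A = 10%, O = 40%; early = days 1–119, late = days 240–363, spread = days 1–363, completers at day 364).

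| AE stops | Other stops | Mean 1 − KM | Mean cumulative incidence |
|---|---|---|---|
| early | late | 9.94% | 9.94% |
| early | spread | 10.89% | 10.13% |
| spread | spread | 13.04% | 10.12% |
| late | early | 16.72% | 10.04% |

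The first and last rows reproduce the two limits in Step 2. The cumulative incidence equalled the crude share in every case, because each subject is followed to discontinuation or week 52.

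**Step 4: comparison of sequences.** Take two sequences with the same A = 10%, one with O = 20% and one with O = 40%. Under constant hazards their curves end at 11.2% and 12.9%. The gap of 1.7 points comes only from other dropout.

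**The case against.** The strongest reply is that this is one sentence in a descriptive efficacy section, with no hypothesis or decision attached, and that the share of interest is already tabulated under SAP 3.3 and 3.9.1. Censoring other causes is a recognised cause-specific display. Neither document says that a week-52 value of one minus Kaplan-Meier will be tabulated for the AE endpoint, and Protocol 14.5 does not name an AE-specific plot. On this view a footnote would do.

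Much of that stands, and it limits the point. Three stronger readings are tempting but unsupported:

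- A reader might infer that the main tolerability result is biased. The documents place time to discontinuation among the efficacy endpoints in the FAS. Tolerability is analysed under safety, in the Safety Population, with crude percentages that do not have this problem.
- A reader might infer a fixed overstatement. No rates are given, and timing matters. With AE stops spread over the first 13 weeks and other stops over 52 weeks, 10% AE discontinuation reads as only 10.4% at 40% total and 10.7% at 60%.
- A reader might infer that curves for the separate reasons will sum to more than the all-cause curve. Only one cause-specific curve is planned, so there is no such set to add.

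The estimator problem remains. Protocol 14.5 names Kaplan-Meier as the way to estimate the discontinuation rate, so reading the AE curve as a share is the natural reading. The crude tables show the share at the end but not its time course, and they do not tell the reader why the curve disagrees with them.

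**Conclusion.** The point holds for the AE-specific curve only. The direction is a property of the estimator: one minus Kaplan-Meier is never below the cumulative incidence, and is above it whenever a non-AE stop precedes an AE stop. Its size cannot be fixed from the documents. It rests on the assumed shares and on timing, as tabulated above, and for a 10% AE share it is 1 to 4 percentage points under constant hazards at 30% to 60% total discontinuation.

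The consequence is a secondary display that can mislead and can conflict with the disposition and AE tables. No primary result is wrong, and the all-cause curve is unaffected.

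The analysis set is a separate source of mismatch. The FAS requires a postbaseline PANSS, first scheduled at week 4 (Protocol Table 3), so a subject who stops early for an AE without a PANSS at early termination is left out. That can lower the AE figure. It may partly offset the excess, but it does not correct it.

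**What to change.** In SAP 3.8.2, replace Kaplan-Meier for the AE endpoint with the Aalen-Johansen cumulative incidence. Treat discontinuation for any non-AE reason as a competing event, censor completers at last dose, and present the result by treatment sequence and overall. Keep Kaplan-Meier for all-cause discontinuation.

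Preferably run the AE analysis in the Safety Population. With the same population, and the same rule for attributing a stop to an AE, the week-52 value should agree with the AE-discontinuation table. In the FAS it may still differ, for the reason given above. Since Protocol 14.5 puts this endpoint in the FAS, record the change of population in SAP section 5, which currently reports no major departures.

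The cost is a sentence in the SAP, an adjusted output shell and a standard procedure. No new data are needed. If the sponsor keeps the Kaplan-Meier curve, the minimum is a footnote saying that it does not estimate the share of subjects who stop for an AE and pointing to the crude table.
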